9.6.3 Breaking the Study Blind/Subject Code

For the final analysis, the treatment codes for all subjects will be released to ACADIA after all subjects have completed the study and the clinical database is locked.

Unblinding of individual treatment assignment during the study is discouraged. The Investigator at a site may break the blind for a given subject in the event of a medical emergency, where knowledge of the subject's treatment assignment (pimavanserin or placebo) must be known in order to facilitate appropriate emergency medical treatment. The Investigator should attempt to contact the study Medical Monitor before unblinding a subject's treatment identity in order to obtain concurrence that unblinding a subject's treatment assignment is necessary. Details of the process to be followed are provided in a separate IRT Manual.

10 SOURCE DOCUMENTS AND ACCESS TO SOURCE DATA/DOCUMENTS

10.1 Case Report Forms and Data Verification

Subject data required by this protocol are to be recorded in an electronic data capture (EDC) system on electronic case report forms (eCRFs). The Investigator and his/her site personnel will be responsible for completing the eCRFs. The Investigator is responsible for the accuracy and reliability of all the information recorded on the eCRFs. All information

requested on the eCRFs needs to be supplied, including subject identification date(s), assessment values, etc. Any omission or discrepancy will require explanation. All information on eCRFs must be traceable to source documentation at the site.

The study monitors will be responsible for reviewing and verifying the data recorded on the eCRFs, utilizing the source documentation, and will query discrepant findings. The Investigator and site personnel will be responsible for answering all queries. The eCRFs will be submitted to ACADIA or its designee for quality assurance review and statistical analysis. A copy of the final eCRFs will be retained by the Investigator, who must ensure that the copy is stored in a secure place.

10.2 Source Documentation

All study specific medical information obtained at each study visit must be recorded in the subject's record (source documentation) in real time as it is collected, and then entered into a validated EDC database by trained site personnel. The source documentation may consist of source notes captured by site personnel as well as laboratory reports, ECG reports, and electronic source data.

11 QUALITY ASSURANCE AND QUALITY CONTROL

ACADIA and/or designee representatives and Regulatory Authority inspectors are responsible for contacting and visiting the Investigator for the purpose of inspecting the facilities and, upon request, inspecting the various records of the study (e.g., eCRFs and other pertinent data) provided that subject confidentiality is respected.

ACADIA and/or designee monitor is responsible for inspecting the eCRFs at regular intervals throughout the study to verify adherence to the protocol; completeness, accuracy, and consistency of the data; and adherence to local regulations on the conduct of clinical research. The monitor should have access to subject medical records and other study-related records needed to verify the entries on the eCRFs.

The Investigator agrees to cooperate with the monitor to ensure that any problems detected in the course of these monitoring visits are resolved.

In accordance with ICH Guidance on GCP and ACADIA's audit plans, a certain percentage of sites participating in this study will be audited. These audits may include a review of site facilities (e.g., pharmacy, drug storage areas, and laboratories) and review of study-related records may occur in order to evaluate the study conduct and compliance with the protocol, ICH Guidance on GCP, and applicable regulatory requirements.

ACADIA and/or designee representatives, regulatory authority inspectors and IRB/IEC representatives who obtain direct access to source documents should also respect subject

confidentiality, taking all reasonable precautions in accordance with applicable regulatory requirements to maintain the confidentiality of subjects' identities.

12 ETHICS/PROTECTION OF HUMAN SUBJECTS

12.1 Ethical Standard

The study will be conducted in compliance with the protocol, the Declaration of Helsinki, ICH principles of GCP, and other applicable regulatory requirements.

The study will be performed in accordance with HIPAA regulations, FDA GCP Regulations (US CFR 21 parts 50, 54, 56, and 312), and ICH GCP Guidelines (E6) and clinical safety data management (E2A).

In accordance with Directive 75/318/EEC, as amended by Directive 91/507/EEC, the final clinical study report (CSR) will be signed by an Investigator and/or Coordinating Investigator who will be designated prior to the writing of the CSR.

12.2 Institutional Review Board/Independent Ethics Committee

The Principal Investigator or designee will provide the IRB/IEC with all requisite material, including a copy of the protocol, informed consent, and any subject information or advertising materials. The study will not be initiated until the IRB/IEC provides written approval of the protocol and the informed consent and until approved documents have been obtained by the Principal Investigator and copies received by the ACADIA. All amendments will be sent to the IRB/IEC for information (minor amendment) or for submission (major amendment) before implementation. The Principal Investigator will supply the IRB/IEC and the ACADIA with appropriate reports on the progress of this study, including any necessary safety updates, in accordance with the applicable government regulations and in agreement with policy established by the ACADIA.

12.3 Informed Consent Process

Properly executed, written informed consent must be obtained from each subject or subject's legally authorized representative prior to initiating screening evaluations required by this protocol. The Informed Consent must at a minimum include the elements of consent described in the ICH guidance on GCP and the US CFR 21 part 50.25. Informed consent must be obtained from the subject's legally authorized representative with the subject's assent if the subject is deemed not competent to provide informed consent.

A copy of the ICF planned for use will be reviewed by ACADIA (or designee) for acceptability and must be submitted by the Investigator, together with the protocol, to the appropriate IRB/IEC for review and approval prior to the start of the study at that investigational site. Consent forms must be in a language fully comprehensible to the

prospective subject. The Investigator must provide ACADIA (or designee) with a copy of the IRB/IEC letter approving the protocol and the ICF(s) before the study drug supplies will be shipped and the study can be initiated.

The consent form must be revised if new information becomes available during the study that may be relevant to the subject. Any revision(s) must be submitted to the appropriate IRB/IEC for review and approval in advance of use.

12.3.1 Consent/Assent and Other Informational Documents Provided to Subjects

The subject must be given a copy of the signed informed consent.

12.3.2 Consent Procedures and Documentation

It is the Investigator or designee's responsibility to obtain written informed consent from the subject after adequate explanation of the aims, methods, anticipated benefits, and potential hazards of the study. The subject must be given ample time to decide about study participation and opportunity to inquire about details of the study. The IRB/IEC-approved consent form must be personally signed and dated by the subject and by the person who conducted the informed-consent discussion. The Investigator or appropriate site personnel must document the details of obtaining informed consent in the subject's study documents. The subject must be given a copy of the signed informed consent and the original maintained in the designated location at the site.

12.4 Subject and Data Confidentiality

The Investigator must ensure that each subject's anonymity is maintained as described below. On the eCRFs or other documents submitted to ACADIA and/or designee, subjects must be identified by a Subject Identification Number only. Documents that are not for submission to ACADIA and/or designee (e.g., signed ICFs) should be kept in strict confidence by the Investigator in compliance with Federal regulations or other applicable laws or ICH Guidance on GCP.

12.5 Research Use of Stored Human Samples

Each time that blood samples are drawn for the analysis of plasma concentrations of pimavanserin, AC-279, and concomitant SSRI/SSNI antidepressants, two aliquots of plasma will be sent to the central lab from the same sample. One of these aliquots will be used for the above analysis, and the second aliquot will be retained at the central lab until the study is completed for any repeat testing that may be needed. All retained plasma samples will be destroyed after completion of the clinical study report (CSR).

12.6 Future Use of Stored Specimens

Not applicable; see Section 12.5 above.

13 DATA HANDLING AND RECORD KEEPING

13.1 Data Collection and Management Responsibilities

All documents required for the conduct of the study as specified in the ICH GCP guidelines will be maintained by the Investigator in an orderly manner and made available for monitoring and/or auditing by the ACADIA and regulatory agencies.

The Investigator and institution must permit authorized representatives of ACADIA and/or designee (including monitors and auditors), and the regulatory agency(s) (including inspectors), and the IRB/IEC direct access to source documents (such as original medical records). Direct access includes permission to examine, analyze, verify, and reproduce any records and reports that are needed for the evaluation of the study. The Investigator must ensure the reliability and availability of source documents from which the information on the eCRF was derived.

13.2 Study Records Retention

Investigators are required to maintain all essential study documentation as per ICH GCP guidelines. This includes, but is not limited to, copies of signed, dated and completed eCRFs, documentation of eCRF corrections, signed ICFs, subject-related source documentation, and adequate records for the receipt and disposition of all investigational drug. Investigators should maintain all essential study documentation, for a period of at least two years following the last approval of marketing application in an ICH region (US, Europe, and Japan), or until at least two years after the drug investigational program is discontinued, unless a longer period is required by applicable law or regulation. Only ACADIA can notify an Investigator or vendor when any records may be discarded. Investigators should contact ACADIA before destroying any files.

13.3 Protocol Changes

13.3.1 Protocol Amendments

Changes to the protocol may be made only by ACADIA (with or without consultation with the Investigator). All protocol modifications must be submitted to the site IRB/IEC in accordance with local requirements and, if required, to the Regulatory Authority, as either an amendment or a notification. Approval for amendments must be awaited before any changes can be implemented, except for changes necessary to eliminate an immediate hazard to study subjects, or when the changes involve only logistical or administrative aspects of the study. No approval is required for notifications.

13.3.2 Protocol Exceptions and Deviations

No prospective entry criteria protocol deviations are allowed; all subjects must meet all eligibility criteria in order to participate in the study.

Protocol waivers for eligibility will not be granted by ACADIA under any circumstances. If, during the course of a subject's post-randomization participation in the study it is discovered that the subject did not meet all eligibility criteria, s/he will be discontinued, unless the discontinuation presents an unacceptable medical risk. The justification to allow the subject to continue in the study will be made by ACADIA, with medical input from the Investigator, and will be documented. If allowed to remain in the study, this will be reported as a major protocol deviation and not a waiver. All follow-up safety assessments must be completed and documented as outlined in the protocol. The Investigator must report any protocol deviation to ACADIA and, if required, to the IRB/IEC in accordance with local regulations, within reasonable time.

13.4 Publication and Data Sharing Policy

All publication rights are delineated in the Clinical Study Agreement and/or other separate agreements with the Investigator and/or Institution, as applicable.

14 CONFLICT OF INTEREST POLICY

14.1 Finance, Insurance, and Indemnity

Arrangements for finance, insurance and indemnity are delineated in the Clinical Study Agreement and/or other separate agreements with the Investigator and/or Institution, as applicable.

Appendix C: Sample Assessment Scales88

Appendix A: Prohibited and Restricted Medications

Subjects taking prohibited medications at study entry will not be randomized. Subjects taking prohibited medications during the trial will be discontinued, unless the discontinuation presents an unacceptable medical risk. The justification to allow the subject to continue in the trial will be made by the Sponsor/Medical Monitor with medical input from the Investigator, and will be documented. If allowed to remain in the trial, this will be reported as a major protocol deviation and not a waiver.

The table below lists prohibitions and restrictions by medication class, including representative medications within class. Medications within each class include but are not limited to the examples listed in this table. Any questions regarding prohibited and restricted medications should be discussed with the Medical Monitor or appropriate designee.

Medication Class	Examples ¹	Prohibition/restrictions
Antipsychotics other than pimavanserin	
 • aripiprazole • brexpiprazole • haloperidol • olanzapine • risperidone 	All antipsychotics are prohibited
Anticonvulsant and mood stabilizers	
 • carbamazepine • lamotrigine • lithium • phenytoin • valproate • topiramate • gabapentin • pregabalin 	
 • Must be washed out prior to Baseline or for 5 half-lives of drug prior to Baseline • Prohibited throughout the study
Antidepressants other than background therapy (see Inclusion Criterion #6)	
 • trazodone • TCAs – including those used for pain, migraines • mirtazapine • bupropion 	Prohibited at Baseline and throughout the study
Anxiolytics	benzodiazepines	
 • Must be washed out prior to Baseline or for 5 half-lives of drug prior to Baseline • Prohibited throughout the study
Stimulants	methylphenidate	Prohibited at Baseline and throughout the study
Non-stimulant ADHD medications	
 • Atomoxetine • guanfacine 	Prohibited at Baseline and throughout the study
Serotonin antagonists	
 • cyproheptadine • fluvoxamine • mianserin • mirtazepine • nefazodone • trazodone 	
 • Prohibited throughout the study • Must be discontinued at least 3 weeks prior to the Baseline visit

Medication Class	Examples ¹	Prohibition/restrictions
Antiarrhythmic drugs	
 • ajmaline • amakalant, semantilide • amiodarone • bretylium • disopyramide • dofetilide • dronedarone • flecainide • ibutilide • procainamide • propafenone • quinidine • sotalol, d-sotalol 	Prohibited at Baseline and throughout the study
Antimicrobials, antifungals, and antimalarials	
PROHIBITED
 
 • azithromycin • clarithromycin • erythromycin • levofloxacin • moxifloxacin • pentamidine 	Clarithromycin, erythromycin, levofloxacin, moxifloxacin, and pentamidine are prohibited at study entry and throughout the study
	
RESTRICTED
 
 • arteminol/piperaquine • azithromycin • bedaquiline • ciprofloxacin • gemifloxacin • norfloxacin • ofloxacin • quinine • roxithromycin 	
 • Ciprofloxacin and azithromycin are restricted • Prohibited at baseline but may be used during the course of the study to treat a bacterial infection (e.g., urinary tract infection, respiratory infection), post-Baseline at the discretion of the PI. • Arteminol/piperaquine, bedaquiline, gemifloxacin, norfloxacin, ofloxacin, quinine, roxithromycin are only allowed under the following conditions: 
 ○ The subject has a Baseline ECG with a QTcF <425 ms OR ○ The subject has a QTcF <450 ms at Baseline AND QRS duration ≥120 ms
Hypnotics	
 • doxepine • diphenhydramine • eszopiclone • gabapentin • mirtazepine • quetiapine • ramelteon • trazadone • zaleplon • zolpidem 	
 • Medications should be washed out during Screening period • Prohibited at Baseline and throughout the study • No sedating antihistamines allowed during the study

Medication Class	Examples ¹	Prohibition/restrictions
Herbal and nutritional supplements	
 • St. John's wart • S-adenosylmethionine (SAM-E) • valerian root • melatonin • L-tryptophan 	Prohibited at Baseline and throughout the study
Sedating antihistamines for sleep	
 • diphenhydramine • dimenhydrinate • hydroxyzine • promethazine 	Prohibited at Baseline and throughout the study
Opioid Analgesics	
 • Codeine • Oxycodone • Tramadol • Morphine • Methadone 	Prohibited throughout the study

¹Medications within each class include but are not limited to the examples listed in this table.

Appendix B: Prohibited and Restricted Concomitant Medications: Inhibitors and Inducers of Cytochrome P450 Enzyme 3A4

The information presented here is intended to provide guidance and does not constitute an exhaustive list of strong and moderate CYP 3A4 enzyme (CYP3A4) inhibitors and inducers. Any questions should be discussed with the Medical Monitor or appropriate designee.

Subjects who take prohibited concomitant medications during the trial will be discontinued, unless the discontinuation presents an unacceptable medical risk. The justification to allow the subject to continue in the trial will be made by the Sponsor with medical input from the Investigator, and will be documented. If allowed to remain in the trial, this will be reported as a major protocol deviation and not a waiver.

Inhibitors of CYP3A4 are to be stopped at least 7 days or 5 half-lives prior to study drug administration, whichever is longer. Inducers of CYP3A4 are to be stopped 30 days or 5 half-lives prior to study drug administration, whichever is longer. Moderate inhibitors and inducers of CYP3A4 may be allowed but should be used with caution. The metabolism of pimavanserin is affected by strong CYP3A4 inhibitors, resulting in an increase in maximum plasma concentration (C_{max}) and area under the plasma concentration-time curve (AUC) of approximately 3-fold.

STRONG INHIBITORS
	
Boceprevir (Victrelis[®]) Clarithromycin (Biaxin[®]) Cobicistat (part of Stribild[®]) Conivaptan (Vaprisol[®]) Fluvoxamine (Luvox[®]) Grapefruit juice^a Indinavir (Crixivan[®]) Itraconazole (Sporanox[®]) Ketoconazole (Nizoral[®]) Lopinavir and Ritonavir (Kaletra[®]) Mibefradil (Posicor[®]) Nefazodone (Serzone[®]) Nelfinavir (Viracept[®]) Posaconazole (Noxafil[®]) Quinupristin (Synercid[®]) Ritonavir (Norvir[®], part of Viekira Pak[™]) Saquinavir (Invirase[®]) Telaprevir (Incivek[®]) Telithromycin (Ketek[®]) Voriconazole (Vfend[®])
	
MODERATE INHIBITORS
	
Amprenavir (Agenerase[®]) Aprepitant (Emend[®]) Atazanavir (Reyataz[®]) Ciprofloxacin (Cipro[®]) Darunavir/ritonavir (Prezista[®]/Ritonavir) Diltiazem Erythromycin (Erythrocin[®] Lactobionate) Fluconazole (Diflucan[®]) Fosamprenavir (Lexiva[®]) Grapefruit juice^a Imatinib (Gleevec[®]) Verapamil (Calan[®])

---------------------------------	---	-----------------------------------	---

STRONG INDUCERS	Avasimibe Carbamazepine (Tegretol [®]) Phenobarbital (Luminal [®] , Solfoton [®]) Phenytoin (Dilantin [®]) Rifampin (Rifadin [®] , Rifadin IV [®] , Rimactane [®]) St. John's Wort	MODERATE INDUCERS	Bosentan (Tracleer [®]) Efavirenz (Sustiva [®]) Etravirine (Intelence [®]) Modafinil (Provigil [®]) Nafcillin (Unipen [®] , Nallpen [®])
----------------------------	--	------------------------------	---

^a The effect of grapefruit juice varies widely among brands and is concentration-, dose-, and preparation-dependent. Studies have shown that it can be classified as a “strong CYP3A inhibitor” when a certain preparation was used (e.g., high dose, double strength) or as a “moderate CYP3A inhibitor” when another preparation was used (e.g., low dose, single strength). (FDA Drug Development and Drug Interactions

<http://www.fda.gov/Drugs/DevelopmentApprovalProcess/DevelopmentResources/DrugInteractionsLabeling/ucm093664.htm#classInhibit>)

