6.7 Concomitant Medications, Treatments, and Procedures

All medications used up to 4 weeks prior to Baseline (Week 0) through the 30-day Follow-up Visit should be recorded.

In order to ensure that appropriate concomitant therapy is administered, it is essential that subjects be instructed not to take any medication without prior consultation with the Investigator (unless the subject is receiving treatment for a medical emergency).

The Investigator may prescribe appropriate medication to treat AEs. ACADIA and the Investigator, or designee, will confer to determine whether it is appropriate to continue such a subject in the study if a prohibited medication is prescribed.

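### Appendix A lists azithromycin as prohibited although its own rule text makes it restricted, and it gates seven QTcF-restricted antimicrobials on the pre-dose Baseline ECG alone

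*Protocol*

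**What the plan says.** **Azithromycin.** In the antimicrobial rows of Protocol Appendix A, the prohibited example list has six agents, azithromycin among them. The rule beside that list names five: "Clarithromycin, erythromycin, levofloxacin, moxifloxacin, and pentamidine are prohibited at study entry and throughout the study". Azithromycin appears again in the restricted example list, where the rule reads "Ciprofloxacin and azithromycin are restricted". That rule bars both drugs at Baseline and then leaves use for a bacterial infection to the investigator's discretion.

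**The seven gated agents.** Arteminol/piperaquine, bedaquiline, gemifloxacin, norfloxacin, ofloxacin, quinine and roxithromycin are allowed under either of two conditions. The first is "The subject has a Baseline ECG with a QTcF <425 ms". The alternative, which serves subjects with a wide QRS complex, is worded "The subject has a QTcF <450 ms at Baseline AND QRS duration ≥120 ms".

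**Consequence of a prohibited drug.** The opening of Appendix A states: "Subjects taking prohibited medications during the trial will be discontinued, unless the discontinuation presents an unacceptable medical risk". A subject kept in under that exception is recorded as a major deviation.

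**QT information elsewhere.**
- Protocol Section 1.3.1 gives a mean prolongation of about 5-8 ms. It advises against pimavanserin in known QT prolongation and in combination with QT-prolonging drugs, certain antibiotics included.
- Exclusion 18 (Section 4.2) sets entry limits of 450 ms, or 470 ms if QRS is at least 120 ms, on Screening and Baseline ECGs.
- ECGs are repeated at Weeks 1, 5, 6 and 10.
- SAP Section 14.4 flags QTc above 500 ms or a rise above 60 ms, for tables and listings.

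**The concern.** The azithromycin entry is a contradiction inside an operating rule. Two sites treating the same infection could act in opposite ways. One might lose the subject or record a major deviation; the other would carry on as the rule text permits.

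The ECG condition is a gap rather than a contradiction. The decision to add one of the seven agents is made on treatment, but the only number a site is told to check predates the study drug. Investigators receive the masked protocol (Section 9.6.1), so they will read Baseline as Week 0. For the roughly 49 subjects switched to pimavanserin at Week 5, that ECG is 5 to 10 weeks old throughout their exposure. A subject whose QTcF has become prolonged on treatment still meets the written condition, even though a later tracing may already be on file.

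**Working it through.** **1. Azithromycin, side by side**

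| Place in Appendix A | Status of azithromycin |
|---|---|
| Prohibited example list | Listed (one of 6) |
| Rule text beside it | Omitted (names the other 5) |
| Restricted example list | Listed |
| Rule text beside it | Restricted; post-Baseline use at investigator discretion |

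Both pieces of rule text agree with each other and with the restricted list. The prohibited list is the odd one out, so that entry is the likely error.

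**2. Search for an on-treatment QTcF limit**

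| Place | Finding |
|---|---|
| Protocol 4.2, exclusion 18 | Numeric, but Screening and Baseline only |
| Protocol 4.4, withdrawal | Adverse event, physician decision and others; no QTcF value |
| Protocol 5.1.5, dose changes | Missed doses only |
| Protocol 6.3.9, ECGs | Clinician review; no action limit |
| Protocol 1.3.1, risks | Qualitative advice; no value |
| SAP 14.4 | >500 ms and >60 ms rise; reporting only |

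No subject-management rule gives an on-treatment limit.

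**3. Margin already built in**

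450 − 425 = 25 ms (first route) and 470 − 450 = 20 ms (second route). Both exceed the mean effect of 5-8 ms.

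**4. Size, illustration only**

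The documents give no Baseline QTcF distribution, no SD of change and no rate of antimicrobial use, so the share of subjects affected cannot be computed. Assume that individual change is normal with SD 10 or 20 ms, and that QTcF is reported in whole ms. Take a mean change of 5 or 8 ms on pimavanserin and 0 on placebo, before any effect of the antimicrobial:

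P(QTcF > limit) = 1 − Φ((limit + 0.5 − Baseline − mean) / SD)

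Example: limit 450, Baseline 424, mean 8, SD 20 gives (450.5 − 432)/20 = 0.925, so P = 17.7%.

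| Baseline (ms) | Limit (ms) | Pimavanserin | Placebo |
|---|---|---|---|
| 400 | 450 | <0.1% to 1.7% | <0.1% to 0.6% |
| 410 | 450 | <0.1% to 5.2% | <0.1% to 2.1% |
| 424 (top of first route) | 450 | 1.6% to 17.7% | 0.4% to 9.3% |
| 449 (top of second route, QRS ≥120 ms) | 470 | 5.0% to 25.0% | 1.6% to 14.1% |

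Against 500 ms on pimavanserin, the maximum is 0.03% from 424 ms and 1.5% from 449 ms. For a rise above 60 ms it is 1 − Φ((60.5 − 8)/20) = 0.4%. The drug shift applies to about 47 + 49 = 96 of 188 subjects.

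**5. How old the latest scheduled ECG can be**

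SAP Table 2 target days give 36 − 8 = 28 days (Weeks 1 to 5) and 71 − 43 = 28 days (Weeks 6 to 10). With both ±3-day windows this becomes 28 + 6 = 34 days. At Week 1 the active metabolite (half-life about 200 h, Protocol 1.1.1) has reached 1 − 2^(−168/200) = 44% of steady state, assuming simple accumulation.

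**6. What the same check would do to ciprofloxacin and azithromycin**

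These two carry no 425 ms cut-off, so subjects up to the 450 ms entry limit (QRS <120 ms) come into play. Under the same assumptions, the chance of exceeding 450 ms is 29-45% on pimavanserin (15-30% on placebo) from a Baseline of 440 ms. From 449 ms it is 57-74% (44-47% on placebo).

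**The case against.** The strongest reply is that the plan already protects subjects. Section 1.3.1 advises against combining pimavanserin with QT-prolonging drugs. Section 6.7 says "it is essential that subjects be instructed not to take any medication without prior consultation with the Investigator", and it has the sponsor and investigator confer on continuation if a prohibited drug is prescribed. A clinician reads every ECG (6.3.9), withdrawal by physician decision is available (4.4), and unscheduled visits are allowed (6.5.15). Appendix A adds "Any questions regarding prohibited and restricted medications should be discussed with the Medical Monitor or appropriate designee". Nothing prevents a fresh ECG before prescribing, so the 34-day figure is a worst case for scheduled visits. Much of the crossing of 450 ms is ordinary variability: from 424 ms, placebo already reaches up to 9.3%. And the Baseline condition is a minimum, not an instruction to prescribe.

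All of that stands, and it keeps the ECG point small. It does not remove it: none of these safeguards stops a subject with on-treatment prolongation from meeting the written condition.

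On azithromycin, the reply is that the rule text shows the answer and the Medical Monitor can be asked. That makes the correction easy; it does not make the two statements consistent.

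A reader might infer three stronger things that the documents do not support:
- *That QT risk is unmanaged.* The margins and general safeguards above say otherwise.
- *That the azithromycin entry must cost subjects.* Appendix A has a medical-risk exception, and Section 6.7 requires a discussion first.
- *That ciprofloxacin and azithromycin need the same ECG check.* The plan leaves them to investigator discretion, and Appendix B says of moderate CYP3A4 inhibitors, ciprofloxacin among them: "Moderate inhibitors and inducers of CYP3A4 may be allowed but should be used with caution". Near the entry limit a 450 ms check would often block their use (step 6), largely through variability. That is a trade-off for the clinical team, not a defect.

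**Conclusion.** The azithromycin conflict is an error on the face of Appendix A and needs no assumption about rates. The rule text settles which entry is wrong.

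The Baseline-only gate on the seven agents is a cheap safety improvement with a small expected effect. The existing margins cover the mean drug effect, and crossing 500 ms is rare under every assumption tried. Crossing 450 ms, or 470 ms with a wide QRS, becomes material only for subjects who start close to a cut-off. These sizes rest on assumed SDs of 10-20 ms and a normal distribution. They are conditional on a subject being considered for one of the seven agents, and the documents give no rate for that. Manuals outside the protocol and SAP could not be checked. Worth considering; no effect on the efficacy analysis is claimed.

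**What to change.** 1. Delete azithromycin from the prohibited example list in Appendix A. This costs nothing beyond the edit and follows the rule text already there.
2. Keep both Baseline cut-offs. For the seven gated agents only, and for all subjects regardless of arm, add: *and the most recent on-study ECG, scheduled or unscheduled, is not above the exclusion 18 limits (QTcF 450 ms, or 470 ms if QRS is at least 120 ms)*. Applying it to everyone avoids revealing treatment or the Stage 2 re-randomization.
3. Leave ciprofloxacin and azithromycin at investigator discretion.

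Cost: one appendix wording change, no new scheduled ECG and no SAP change. A few subjects, mainly those with a Baseline QTcF near a cut-off, will need another antimicrobial. The check is imperfect: the latest scheduled ECG may be up to about 34 days old, it is off-drug until Week 6 for subjects switched at Week 5, and at Week 1 the metabolite is well short of steady state. That is why the Baseline margin stays and the new condition only supplements it.
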